8.1 Primary Analysis

Primary analysis: The primary analysis will be a modified intention to treat analysis that will include all patients who were randomized and began treatment. Because of the double-blind design of the study, this analysis tests the primary study hypothesis, and with slightly higher power than an analysis of all randomized patients. The primary analysis of this endpoint will use multiple imputation methods to account for missing outcome data, and logistic regression adjusting for site, to compare the combined TXA treatment arms to the placebo arm and estimate the adjusted odds ratio to describe the strength of the association between TXA treatment and favorable GOS-E at 6 months^{104,105,106}. To reduce the chances that we will fail to demonstrate a possible treatment effect in this phase II study, a one-sided hypothesis test at the 0.1 level will be performed to compare the combination of the two treatment groups to the placebo group. To evaluate the possibility that TXA treatment reduces the proportion of patients with good neurologic outcome at six months, a one-sided test at the .025 level will be conducted.

- Safety population: Analysis of treatment safety will be conducted on all patients who had the study drug connected to their IV line. Safety data will be reported on a regular basis to the Resuscitation Outcomes Consortium Data Safety Monitoring Board (ROC DSMB).

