Sample size: The total sample size in the primary analysis population is 963 (321 per group), which will allow for 80% power to detect a 7.1% absolute increase in the proportion of patients with a favorable long-term neurological outcome as determined by the GOS-E 6 months after injury comparing patients who receive TXA to patients who receive placebo, using a one-sided, level 0.1 test. It will allow for 80% power to detect an absolute decrease of 9.5% in the proportion of patients with a favorable long-term neurologic outcome comparing patients who receive TXA to patients who receive placebo, using a one-sided, level 0.025 test.

Statistical analysis of primary hypothesis: Modified intention-to-treat analysis using logistic regression to test for association and estimate the strength of the association of treatment group with a favorable 6-month outcome (defined as a GOS-E > 4), after adjustment for study site.

Human subjects protection: This study qualifies for the exception from informed consent (EFIC) required for emergency research outlined in FDA regulation 21CFR50.24. EFIC applies because of life-threatening situation, intervention must be administered before consent is feasible, no reasonable way to identify prospectively individuals at risk, patients have the prospect of benefit from the treatment, and the research could not practically be carried out without the waiver of consent.

1. Overview

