4.3 Inclusion Criteria

Subjects must meet ALL of the following:

1. Blunt or penetrating traumatic mechanism consistent with traumatic brain injury
2. Prehospital GCS score ≤ 12 at any time prior to randomization and administration of sedative and/or paralytic agents
3. Prehospital SBP ≥ 90 mmHg prior to randomization
(SBP < 90 mmHg has been used as the entry criteria for nearly all major investigations studying the treatment of shock.^{67,68,69,70} Furthermore, prehospital hypotension has been associated with a dramatic increase in morbidity and mortality following severe TBI including a two-fold increase in the incidence of severe disability and death.⁷¹)
4. Prehospital intravenous (IV) access
5. Estimated Age ≥ 15 (or estimated weight > 50 kg if age is unknown)
(Enrollment will be restricted to age ≥ 15 years or > 50 kg if age is unknown as these adolescents are of appropriate size to receive the full dose of TXA).
6. EMS transport destination based on standard local practices determined to be a participating trauma center
(Patients who are temporarily stabilized at an outside facility and transported to a participating center will be considered 'modified scene patients' and will remain eligible if all other inclusion and exclusion criteria are met).

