5.1 Screening Procedures

Screening will be conducted in the prehospital setting by the initial EMS responder. Prehospital trauma life support interventions focusing on airway, breathing and circulation will be performed and an initial GCS score will be assessed by EMS to determine eligibility. The patient will be considered eligible if the initial GCS is ≤ 12 and the SBP has remained ≥ 90 mmHg prior to randomization, and other inclusion/exclusion criteria are met. If the GCS improves to greater than 12 prior to randomization, the patient will not be randomized. If the initial GCS is > 12 and during transport declines to ≤ 12 prior to administration of sedating and/or paralytic medication, the patient will become eligible if the SBP has remained ≥ 90 mmHg prior to randomization. If the SBP drops below 90 mmHg between randomization and administration of study drug or anytime thereafter, the patient will remain in the study and continue to receive the study drug.

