5.2 Study Procedures

5.2.1 Randomization

Eligible patients will be randomly allocated in a proportion of 1:1:1 bolus/maintenance arm, bolus only arm, and placebo. Randomization assignments will be generated by the ROC DCC. To attempt balance by site, permuted blocks of varying concealed size will be used. Nevertheless, location of the episode and availability of providers determine which agency responds to the episode and the order in which the containers are used cannot be determined a priori. As a result, the randomization will represent a complete randomization rather than a permuted block randomization.

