5.3 Baseline Assessment

The baseline data, including demographics, injury mechanism, prehospital and ED hemodynamic variables, time to definitive care, mode of transport, presence of TBI, and fluids and blood products administered within the first 24 hours after injury will be obtained by the research coordinator as soon as feasible.

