8.2 Pre-Specified Secondary Subgroup Analyses

Secondary analyses of the primary endpoint will additionally adjust for baseline prognostic factors including age, gender, prehospital GCS, mechanism of injury, and injury severity. Analyses for secondary outcomes that are binary will be conducted similarly. Additional secondary analyses of the primary endpoint will compare each treatment group separately to placebo, and the two treatment groups to each other. For quantitative secondary outcomes, linear regression analysis with robust standard errors will be used to test for treatment-placebo differences and to estimate the mean outcome difference associated with treatment, after adjustment for site and prognostic variables. Evidence for modification of the effect of treatment in the efficacy population by the presence or absence of additional prognostic factors will be examined using interaction terms in linear or logistic regression models, and estimated treatment differences will be reported separately in subgroups together with the statistical significance of the associated hypothesis tests for interaction. It is recognized that this study is not powered adequately to detect interactions and thus subgroup analyses will be considered exploratory, generating hypotheses for further study.

A priori subgroup analyses will compare outcome between both the combined and individual TXA treatment groups and the placebo group in:

1. Patients who met all inclusion and exclusion criteria
2. Patients who received the full intervention/placebo
3. Patients who receive the prehospital intervention/placebo only
4. Patients with an ICH on initial head CT and repeat head CT performed within 24 hours
5. Patients with blunt vs. penetrating TBI
6. Patients with Head AIS score ≥ 4
7. Patients with Head AIS score <2 (altered mental status likely secondary to intoxication and not significant TBI)
8. Patients requiring emergent craniotomy
9. Patients stratified by no PRBC received versus 1-9 units PRBC received versus ≥ 10 units PRBC received in the first 24 hours
10. Patient who require TXA administration for hemorrhagic shock after being randomized in the study

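### The primary test adjusts for site only; adding age and prehospital GCS would gain about 1 to 3 points of power at almost no cost, under an assumed prognostic strength

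*Combined protocol and SAP*

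**What the plan says.** The primary analysis in section 8.1 is a multiply imputed "logistic regression adjusting for site, to compare the combined TXA treatment arms to the placebo arm and estimate the adjusted odds ratio". The Summary agrees: it tests the association of treatment group "with a favorable 6-month outcome (defined as a GOS-E > 4), after adjustment for study site".

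Section 8.1 gives the reason for the one-sided 0.1 level of the benefit test: "To reduce the chances that we will fail to demonstrate a possible treatment effect in this phase II study". Harm is tested one-sided at 0.025.

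Other baseline variables come in only under section 8.2: "Secondary analyses of the primary endpoint will additionally adjust for baseline prognostic factors including age, gender, prehospital GCS, mechanism of injury, and injury severity".

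Section 5.2.1 attempts balance by site through permuted blocks, then concedes that the order in which kits are used cannot be controlled: "As a result, the randomization will represent a complete randomization rather than a permuted block randomization".

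Both covariates are collected. Under section 5.1, "an initial GCS score will be assessed by EMS to determine eligibility". Section 5.3 begins its list with "The baseline data, including demographics, injury mechanism, prehospital and ED hemodynamic variables".

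**The concern.** A binary-outcome comparison that leaves out strong baseline predictors gives up power. The plan itself treats age and prehospital GCS as prognostic in section 8.2. Appendix 3 (A. Background and Significance) names age and the GCS motor score, with pupillary reactivity, as the strongest predictors of outcome. Nothing in the allocation scheme balances age or GCS.

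The power calculation in section 7 compares two binomial proportions and takes no credit for covariates. Adjustment would therefore add power beyond the stated 80%, for the harm test as well as the benefit test.

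The section 8.2 model could not be promoted as written. Its covariate list is open-ended. Injury severity has no stated measure or timing and may be scored from in-hospital findings after treatment has started. Prehospital GCS is not a single value: section 4.3 accepts a qualifying score "at any time prior to randomization and administration of sedative and/or paralytic agents", and section 5.1 allows it to rise or fall before randomization.

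**Working it through.** **Inputs from the plan.** 321 placebo and 642 combined TXA (1:1:1 allocation, total 963); 60% favorable on placebo (40% poor, section 7); 67.1% for benefit (+7.1 points) at one-sided 0.10; 50.5% for harm (−9.5 points) at one-sided 0.025.

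**Assumed input.** Age plus prehospital GCS add a Nagelkerke R-squared of 0.05 to 0.10 beyond site.

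**Step 1: reproduce the stated power.** Power = Φ[(|d| − z × SE0)/SE1], where SE0 uses the pooled rate and SE1 the separate rates.

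- Benefit: pooled rate (0.600 + 2 × 0.671)/3 = 0.647; SE0 = 0.0327, SE1 = 0.0330. Φ[(0.071 − 1.2816 × 0.0327)/0.0330] = 0.811.
- Harm: pooled rate (0.600 + 2 × 0.505)/3 = 0.537; SE0 = 0.0341, SE1 = 0.0337. Φ[(0.095 − 1.960 × 0.0341)/0.0337] = 0.798.

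Both match the stated 80%. The detectable benefit without the futility look is 0.0697, against 0.070 in section 8.5.

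**Step 2: analytic gain from a baseline power of 80%.** At a 60% favorable rate the maximum Cox-Snell R-squared is 1 − exp[2(0.6 ln 0.6 + 0.4 ln 0.4)] = 0.74. Nagelkerke 0.05 and 0.10 are therefore Cox-Snell 0.037 and 0.074. The noncentrality is divided by sqrt(1 − R²).

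- Benefit, starting from 1.2816 + 0.8416 = 2.123: at 0.05, 2.123/sqrt(0.963) = 2.164 and power is 81.1% (+1.1); at 0.10, 2.123/sqrt(0.926) = 2.206 and power is 82.3% (+2.3).
- Harm, starting from 1.960 + 0.8416 = 2.802: at 0.05, 2.855 and 81.5% (+1.5); at 0.10, 2.911 and 82.9% (+2.9).

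**Step 3: simulation.** Simulation A has 8 sites (SD 0.25 on the logit scale), complete randomization, integer GCS 3 to 12, and a true age effect flat to 35 and then declining. It is fitted linearly, so the age form is deliberately wrong (6,000 trials per setting). Simulation B uses one normal prognostic score and no site effects (20,000 trials). Simulation C is a further run without site effects (6,000 trials).

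| Gain in power (points) | Benefit, 0.05 | Benefit, 0.10 | Harm, 0.05 | Harm, 0.10 |
|---|---|---|---|---|
| Analytic | 1.1 | 2.3 | 1.5 | 2.9 |
| A | 1.1 | 2.2 | 1.5 | 2.7 |
| B | 1.2 | 1.8 | 1.2 | 2.8 |
| C | 0.8 | 2.3 | 1.0 | 1.9 |

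The standard error of each paired gain is about 0.3 point in A and 0.2 in B. In A, benefit power moves from 81.9% to 83.0% and from 81.4% to 83.6%; harm power moves from 80.3% to 81.7% and from 80.9% to 83.6%. The squared ratio of mean z for benefit is 1.038 and 1.077, that is, about 4% and 8% more patients.

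**Step 4: checks on the downside.**

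- Uninformative covariates (R-squared 0): benefit −0.2 point (SE 0.1), harm +0.1 (SE 0.1).
- Type I error of the adjusted test: 0.101 and 0.102 for benefit, 0.025 and 0.026 for harm.
- Crude futility look at 200 followed by an adjusted final test at Z = 1.266: type I error about 0.099 and 0.098. Benefit power rises from 80.5% to 81.6% at 0.05 and from 81.2% to 83.1% at 0.10.

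**Step 5: 15% missing outcomes with multiple imputation.** This further assumes that discharge status is good in 60% of favorable and 10% of unfavorable cases. Benefit moves from 77.8% to 78.8% and from 77.9% to 79.4%; harm from 74.8% to 75.7% and from 75.2% to 78.2%. The adjusted run also had age and GCS in its imputation model and the site-only run did not, so these figures mix two changes.

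**The case against.** The strongest reply is that nothing is broken. The site-only test is prespecified, valid and correctly powered; site follows from the allocation scheme; and the adjusted analysis is already planned as secondary, so only the ranking would change. All of that is true and limits the point to an optional improvement.

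The gain is also small and rests on an assumed R-squared. With the simulated efficiency ratios, the detectable benefit moves from 7.1 points to 7.1/sqrt(1.038) = 7.0 or 7.1/sqrt(1.077) = 6.8. Several features point to the low end: GCS 3 with no reactive pupil, SBP below 90 and CPR by EMS are excluded, and section 8.2 expects some low scores to reflect intoxication. The only related figure in the documents, 0.214 in Appendix 3, is for age, motor score and pupils against a lethal outcome in 45 severe patients. It does not carry over to age and total GCS here.

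Chance imbalance is not a separate harm. A 1-in-20 imbalance in the age-GCS score is 1.96 × sqrt(1/321 + 1/642) = 0.134 SD. It moves the site-only difference by 1.3 to 1.8 points, but this variation is already inside its standard error of about 3.3 points. The missing-data comparison is not like for like, and the plan does not list its imputation variables, so they may already include age and GCS.

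Finally, adjustment makes the odds ratio conditional on more variables: at R-squared 0.10, about 1.39 against 1.36 for benefit. That needs a companion summary measure, but it does not undo the gain.

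**Conclusion.** The point holds as a modest, optional efficiency gain. If age and prehospital GCS add a Nagelkerke R-squared of 0.05 to 0.10 beyond site, putting them in the primary model raises power by about 1 to 2 points for benefit and 1 to 3 points for harm. The analytic result and three simulations agree on this size. The R-squared range is an assumption, so confidence in the exact figure is medium. The conclusion does not depend heavily on it: with no prognostic information the loss is at most 0.2 point, and type I error stays near nominal, including after the crude futility look. The site-only test remains valid and meets its stated power with complete outcomes.

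**What to change.** Amend section 8.1, section 8.4 and the Summary before unblinding:

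- Fix the primary logistic model as exactly treatment, site, age and prehospital GCS.
- Name one GCS value for the analysis, for example the last recorded before the kit is opened and before any sedative or paralytic agent. This defines a covariate and leaves eligibility unchanged.
- Add pupil reactivity and GCS motor score only if their prehospital capture is confirmed at all sites before the list is closed; sections 5.3 and 5.4 do not list them. Leave out injury severity.
- State one missing-covariate rule for all arms, such as mean fill plus a missing indicator. Age can be estimated or unknown at entry (section 4.3).
- Put age and GCS in the outcome-imputation model.
- Keep the site-only model as a sensitivity analysis, and report a standardized risk difference beside the odds ratio so that the result can be set against the planned 7.1- and 9.5-point differences.
- Leave section 7 and the crude futility look unchanged, and state that the final decision rests on the adjusted test.

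The cost is a short text amendment, two extra terms in the analysis and imputation models, and one added summary measure. Age and GCS need no new data; pupils and motor score would need a check of what is captured.

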8.2 Pre-Specified Secondary Subgroup Analyses

Secondary analyses of the primary endpoint will additionally adjust for baseline prognostic factors including age, gender, prehospital GCS, mechanism of injury, and injury severity. Analyses for secondary outcomes that are binary will be conducted similarly. Additional secondary analyses of the primary endpoint will compare each treatment group separately to placebo, and the two treatment groups to each other. For quantitative secondary outcomes, linear regression analysis with robust standard errors will be used to test for treatment-placebo differences and to estimate the mean outcome difference associated with treatment, after adjustment for site and prognostic variables. Evidence for modification of the effect of treatment in the efficacy population by the presence or absence of additional prognostic factors will be examined using interaction terms in linear or logistic regression models, and estimated treatment differences will be reported separately in subgroups together with the statistical significance of the associated hypothesis tests for interaction. It is recognized that this study is not powered adequately to detect interactions and thus subgroup analyses will be considered exploratory, generating hypotheses for further study.

A priori subgroup analyses will compare outcome between both the combined and individual TXA treatment groups and the placebo group in:

1. Patients who met all inclusion and exclusion criteria
2. Patients who received the full intervention/placebo
3. Patients who receive the prehospital intervention/placebo only
4. Patients with an ICH on initial head CT and repeat head CT performed within 24 hours
5. Patients with blunt vs. penetrating TBI
6. Patients with Head AIS score ≥ 4
7. Patients with Head AIS score <2 (altered mental status likely secondary to intoxication and not significant TBI)
8. Patients requiring emergent craniotomy
9. Patients stratified by no PRBC received versus 1-9 units PRBC received versus ≥ 10 units PRBC received in the first 24 hours
10. Patient who require TXA administration for hemorrhagic shock after being randomized in the study

8.3 Mechanistic Outcomes

Due to the large number of outcomes and potential analyses, results of analyses of these outcomes will be treated as exploratory and will be used to inform the design of future studies that may result in clinical recommendations. These results will be summarized descriptively and will be analyzed using the same methods as for the secondary outcomes in order to give insight into the mechanism(s) underlying the observed treatment effects. Results will be reported using point estimates and the 95% confidence intervals rather than p-values.

8.4 Plan for Missing Data

All possible efforts will be made to avoid missing outcome data. These include collecting detailed contact information from a variety of different sources prior to hospital discharge (address, email, other family members, friends, physicians), contacting the patient/family within one month of discharge to establish a continued relationship, and integrating TXA follow-up with other medical follow-up (e.g. clinic, physical therapy). For the primary analyses, any missing outcomes will most likely be due to study patients withdrawing from participation in post-discharge follow-up or dropping-out. Neurological status at discharge is highly correlated with neurological status at 6 months.¹⁰⁷ Specifically, we anticipate that patients who have a “good outcome” at discharge tend to improve and not get worse and those that have a “poor outcome” tend to remain at the same status or improve. In primary analyses, multiple imputation methods will be used to account for missing outcome data.^{108,109,110} Sensitivity analyses will consider modified worst-case (last observed GOS-E score minus 1) for missing outcomes in all treatment arms, and a modified best-case (last observed GOS-E score plus 1) for missing outcomes in all treatment arms.

8.5 Sequential Monitoring Plan

Because of the fear that selection criteria based only on field data may potentially include subjects who would not be able to benefit from TXA treatment, one formal futility analysis will be conducted based on outcome data from the first 200 subjects in the analysis population and reported to the ROC DSMB, using a Wang-Tsiatis boundary.¹¹¹ The early stopping for futility is described in Table 1. The futility stopping rule would categorize results at the first analysis as futile if the observed crude difference in probabilities of a bad neurologic outcomes (GOSE < 5 at 6 months post injury) corresponded to an absolute increase of 6.8%. As can be seen from the 95% confidence interval, this futility decision would nearly rule out the hypothesized improvement of 7.1%.

Table 1: Protocol Stopping Rule							
		Futility Boundary			Efficacy Boundary		
	N accrued	Z	Crude Diff	Est (95% CI; one-sided P)	Z	Crude Diff	Est (95% CI; one-sided P)
First	200	0.955	.068	-.047 (-.072, .125); P = .82	NA	NA	NA
Second	963	-1.266	-.042	-.048(-.109, .022); P = .10	-1.266	-.042	-.048(-.109, .022); P = .10

Table 2 presents the probability of declaring superiority, futility or inferiority for selected hypothesized values of the true treatment effect. The incorporation of the futility stopping rule affects the power of the study to detect benefit of TXA very little, moving the minimal absolute treatment difference that can be detected with 80% power from -0.070 to -0.071.

Treatment Diff	Pr[superior] (power)	Pr[Futile]	Pr[inferior]
-.071	.80	.20	0
-.05	.59	.41	0
-.03	.35	.64	0
-.02	.25	.75	.01
-.01	.16	.82	.01
0	.10	.88	.02
.01	.06	.90	.05
.02	.03	.89	.09
.05	0	.68	.31
.10	0	.16	.84

8.6 Adverse and Serious Adverse Events

TXA has been in use for decades and the safety profile is well established. Adverse events will be reviewed by the sponsor, which is the ROC DCC, as required by 21 CFR part 312 in addition to other entities delineated. The trial will collect data on adverse events that may be associated with the use of TXA in TBI. These events will be reviewed by an independent medical monitor and reported regularly to the ROC data safety monitoring board (ROC DSMB). The ROC DSMB is a distinct and separate entity from the ROC DCC and functions independently from the sponsor.

While there have been rare cases of thromboembolic events and seizures potentially associated with TXA use, usually at higher doses, there is no evidence that the TXA treatment regimen proposed in this trial is associated with an increased risk of vascular occlusive events or seizures. Nonetheless, data on vascular occlusive events and seizures will be collected as secondary outcomes and will be provided to the independent medical monitor and ROC DSMB for unblinded review as necessary. Emergency unblinding will be immediately available if the primary treatment team determines TXA should be administered based on standard of care (i.e. patients in hemorrhagic shock). While we do not anticipate additional need to perform emergency unblinding, in the event that unblinding is deemed necessary for safety or treatment related decisions during the course of the study, emergency unblinding will be available to the hospital physician.

An adverse event (AE) will be defined as any untoward medical occurrence affecting a trial participant during the course of the trial. A serious adverse event (SAE) will be defined as any medical occurrence that results in death, is life-threatening, requires ICU admission, requires prolongation of existing hospitalization, or results in persistent or significant disability. All members of the patient management team will be instructed as to the

possible adverse events prior to the start of the trial and will be given an emergency contact number to immediately report any suspected adverse event to the site investigators. Any deaths not explained by the injury severity will be reported individually according to regulations regarding serious adverse events. In addition, serious adverse events will be reported in aggregate by blinded treatment group to the medical monitor and ROC DSMB on a regular basis. All adverse events that occur during the study period (after randomization until hospital discharge) will be recorded on the ROC DCC Alert forms found online. All potential adverse events will be reviewed as to the assigned treatment group and further classified by: a) severity (life threatening, serious, non-serious) and b) expected versus unexpected. Expected adverse events, assessed by the site PI, will be monitored by each enrolling site, reported to overseeing agencies as required by federal regulations and local requirements, and reviewed periodically by the ROC DSMB. The ROC DCC will tabulate and report on non-SAEs on a regular basis.

Suspected Unanticipated Serious Adverse Reaction (SUSAR): Unanticipated serious adverse reactions will include potentially related SAEs suspected to be related to study treatment/intervention. The site PI will classify all in-hospital mortality according to underlying and contributing causes most relevant to TBI and other life-saving interventions.

Expected Adverse Events: Common expected adverse events will include: death related to TBI, infectious complications, ventilator assisted pneumonia, acute lung injury, acute respiratory distress syndrome, acute kidney injury, and multiple organ failure. Counts of these will be tabulated and reported to the ROC Data Safety and Monitoring Committee on a regular basis.

SUSAR Reporting Procedure and Databases: In addition to following local reporting procedures, sites will notify the ROC DCC of a SUSAR or possible thrombotic or seizure related death within 3 business days of discovery of the event, and the site will complete an FDA MedWATCH Form within 7 days of notification and within 15 days of notification if the SUSAR is not life threatening. For a SUSAR, the ROC DCC will notify the medical monitor, ROC DSMB, appropriate regulatory agencies (FDA, Health Canada), ROC DCC IRB, site IRBs/Research Ethics Boards (REB), and the Department of Defense (DoD) promptly.

All unanticipated problems involving risk to subjects or others, serious adverse events related to participation in the study and subject deaths related to participation in the study must be promptly reported by [contact]), by email ([contact]), or by [contact]) to the USAMRMC, Office of Research Protections, Human Research Protection Office. A complete written report will follow the initial notification. In addition to the methods above, the complete report will be sent to the U.S. Army Medical Research and Materiel Command, ATTN: MCMR-RP, [name]-us.

Infusion Discontinuation Rules: Any thromboembolic event (MI, PE, ischemic stroke, or symptomatic DVT) or seizure activity will prompt cessation of the infusion and a medical safety review. Further detail regarding specific clinical indications for stopping the study drug early will be provided in the manual of operations.

